Patients undergoing ERCP with native papilla and pancreatobiliary disease who are candidates for ERCP with biliary cannulation are eligible for enrollment. Subjects must meet all inclusion criteria in order to be eligible to participate in the study.

Inclusion Criteria:

Patients undergoing ERCP for cholangiography, bile or tissue sampling from the gallbladder or bile duct, or for treatment of biliary diseases (removal of common bile duct stones, biliary stent placement)

Exclusion Criteria:

Patients who are less than 18 years old

Pregnant patients

Patients who have undergone previous bile duct cannulation or sphincterotomy

Patients who have undergone prior endoscopic balloon dilation or needle-knife fistulotomy

Patients who have undergone gastric surgery (Billroth gastrectomy II, Roux-en-Y gastric bypass)

Patients with acute pancreatitis

Patients who refuse endoscopic intervention

Patients with ampullary tumor, duodenal stenosis, or pre-operatively proven pancreaticobiliary malunion

Subjects will be recruited based upon their need to undergo ERCP for biliary diagnosis or therapy as determined by the principal investigator or sub-investigators. This determination will be made based upon the clinical requirement of endoscopic biliary cannulation. Subjects will be either inpatients or outpatients who require ERCP and bile duct cannulation. The overall sample size will be approximately 248 patients. Pregnant women will not be recruited for participation in this study as ERCP in certain pregnancies may be harmful to the fetus especially during the first trimester. Additionally, minors (age less than 18 years old) and prisoners will not be recruited or enrolled in the study, as these are vulnerable populations who may have a compromised ability to make an informed decision about participation.

Study Title: Comparison between angled-tip and straight-tip guidewire in biliary cannulation: A prospective, randomized trial

Protocol Version Number: Version 1.0 Protocol Date: 08/29/2022

Subject Enrollment

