All patients enrolled in the study will be required to sign an informed consent form to participate in the study as well as for the resultant data to be collected and used for analysis and eventual publication. Consent will be obtained via a paper consent form on the day of procedure by the research team. A copy of the consent form will be made and given to the subject and the original copy will be stored in a secure file on site. All known risks, benefits and alternative therapies will be explained to the patient by either the PI or sub-investigators prior to signing the consent form. The patient will be randomized to a study arm in a 1:1 fashion by a computer-generated random number list via the REDCap Electronic Data capture application after informed consent has been obtained and just prior to the start of the procedure by either the PI or the sub-investigators.

Study Design and Procedures

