The sample size needed to achieve statistical significance for the primary outcome is 248 (207 *1.2) after adding 20% screen failure rate. The power of the study to detect if there is a true difference will be 0.80. It will take approximately six months to reach the target accrual. The variables that need to be collected include demographics, co-morbidities, laboratory values, date of procedure, diagnosis, outcome of procedure (success of cannulation), duration of procedure, post-procedure complications (including post-ERCP pancreatitis) and fellow involvement in procedure. The outcome variables include rate of successful cannulation, and incidence of post-ERCP pancreatitis. Predictor variables include co-morbidities, indication for procedure and fellow involvement in procedure. Potential confounding variables include differing anatomy of papilla amongst subjects, underlying etiology of biliary obstruction (which may be different from suspected pre-procedure diagnosis) or unforeseen biliary pathology which alters procedure. The study endpoints will be achieved by showing a statistically significant difference in the rate of successful cannulation using an angled-wire as compared to a straight wire as defined as a p-value of less than 0.05. The proportion of procedures that are successful in the two treatment arms will be compared using chi squared analysis. Similarly, the rate of development of pancreatitis will be compared using chi squared analysis. The total duration of the procedure will be compared using a T-Test for comparing mean if the data are normally distributed or a Wilcoxon rank sum test if not normally distributed.

Data Management

All data will be collected using the REDCap Data Collection application and will be stored electronically on this platform. Only the PI and sub-investigators will have access to the password encrypted REDCap database. There will be no transmission of the acquired data off site. The data set will not include patient names or other identifiers. Information for this study will be available as required to the FDA, Massachusetts Department of Health, and LHMC IRB. Names of subjects will not be mentioned in publications or case reports.

Study Title: Comparison between angled-tip and straight-tip guidewire in biliary cannulation: A prospective, randomized trial
Protocol Version Number: Version 1.0 Protocol Date: 08/29/2022

Data and Safety Monitoring and Quality Assurance

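### The allowance for 20% screen failure is computed as 207 × 1.2 = 248, which covers only 16.5%, and the plan does not say whether 248 counts consented or randomised patients

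*Combined protocol and SAP*

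**What the plan says.** The Statistical Analysis section derives the sample size in one sentence: "The sample size needed to achieve statistical significance for the primary outcome is 248 (207 *1.2) after adding 20% screen failure rate". It adds: "The power of the study to detect if there is a true difference will be 0.80". The significance criterion is given "as defined as a p-value of less than 0.05", and the primary comparison is described thus: "The proportion of procedures that are successful in the two treatment arms will be compared using chi squared analysis".

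The Participant Selection / Eligibility section repeats the total: "The overall sample size will be approximately 248 patients". It does not say at what stage those patients are counted.

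The Subject Enrollment section says: "The patient will be randomized to a study arm in a 1:1 fashion". That section and the Study Calendar / Schematic / Schedule section both place randomisation after consent and just before the procedure starts. Consented and randomised patients are therefore separate counts. The document gives no separate numbers for patients screened, randomised and analysed, and no rate for loss after randomisation.

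**The concern.** There are two linked problems.

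First, a screen failure rate is ordinarily a share of those who enter screening. To retain a required number after a 20% failure rate, one divides by 0.8. Multiplying by 1.2 gives too small a screening number.

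Second, the sentence treats 248 as the number needed for the primary test and also says that it includes screen failures. Patients who fail screening are not randomised and contribute nothing to the comparison of arms. If 207 is the number needed for the test, 248 can only be a screening or consent number. If 248 is the number to be randomised, an allowance for screen failure has no place in it.

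At stake are the point at which accrual stops, the number who will be compared, and whether a later reader can tell that the trial met its target.

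**Working it through.** **Inputs**

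- Base number 207, inflation factor 1.2, 20% screen failure rate, inflated total 248, power 0.80 and significance level 0.05: all from Statistical Analysis.
- Total of about 248 repeated: Participant Selection / Eligibility.
- 1:1 allocation after consent: Subject Enrollment.
- Two-sided testing: assumed, because sidedness is not stated and the planned test is chi-squared.
- Success rates behind 207: not stated, so 207 itself cannot be reproduced. It is taken as given.

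**Step 1. Reproduce the plan's figure.** 207 × 1.2 = 248.4, written as 248. It reproduces.

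**Step 2. What 248 yields under the stated rate.** 248 × (1 − 0.20) = 198.4, so about 198 patients pass screening. That is about 9 below 207.

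**Step 3. The failure rate that 248 does cover.** 1 − 207/248 = 0.165, or 16.5%.

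**Step 4. The number that retains 207 after 20% fail.** 207/(1 − 0.20) = 258.75, so 259, which is 11 more than 248. For two arms of 104, 208/0.80 = 260.

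**Step 5. Power under each meaning of 248.** Suppose that 207 gives exactly 0.80 at two-sided 0.05. The standardised effect at 207 is then 1.960 + 0.842 = 2.802, and it scales with the square root of the sample size:

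power(n) = Φ(2.802 × √(n/207) − 1.960)

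| Meaning of 248 | Patients compared | Calculation | Power |
|---|---|---|---|
| Consented, 20% fail | 198.4 | Φ(2.802 × 0.979 − 1.960) = Φ(0.783) | about 0.78 |
| Randomised, all analysed | 248 | Φ(2.802 × 1.095 − 1.960) = Φ(1.107) | about 0.87 |

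A two-proportion power calculation, with the effect set so that 207 gives 0.80, returned 0.783 and 0.867 for every assumed control success rate tried from 0.50 to 0.90. The change in power therefore does not depend on the missing success rates. It does depend on 207 being right for 0.80.

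**The case against.** **The 20% may have been meant as an add-on.** The author may have intended extra patients equal to 20% of 207, about 41. Then 248 screened would give 207 randomised, with no shortfall. This is a fair reading of the arithmetic. However, 41 failures among 248 screened is a rate of 16.5%, so the stated rate would need correcting, and 248 would still not be the number needed for the test.

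**The plan may be conservative.** If 248 are to be randomised, the trial exceeds its base number by 41, and power is above the stated 0.80. Nothing in the document rules this out: it speaks of an overall sample size, a sample size needed and a target accrual, and none of these settles the matter. The words "after adding 20% screen failure rate" point towards a count before randomisation, but they do not prove it.

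**The effect is small.** This stands. The worst case is 11 consents and 1.7 percentage points of power, against a total that the eligibility section calls approximate and a failure rate with no stated source. Recruitment could also simply continue until enough patients are randomised.

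**Two stronger inferences are tempting.** A reader might infer that the trial is underpowered, or that it will end about 9 analysable patients short. The document supports that only if 248 counts consented patients, 20% of them fail screening, and 207 gives exactly 0.80. Nor is 20% an allowance for loss of the primary outcome: no such rate is stated, and cannulation success is recorded immediately after the procedure, so little loss among randomised patients is expected. A reader might also infer that the target should simply become 208 randomised. If 248 are meant to be randomised, that would remove 40 patients and bring power down from about 0.87 to about 0.80.

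**Conclusion.** The concern holds in a limited form. For a 20% failure rate among those screened, the inflation should give 259, not 248, and 248 covers only 16.5%. That follows from the plan's own figures and needs no assumption about the treatment effect. It is equally plain that neither section says whether 248 counts consented or randomised patients.

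The consequence depends on the answer: about 198 randomised and power of about 0.78 if 248 are consented, or power of about 0.87 if 248 are randomised. Both power figures rest on two-sided testing at 0.05 and on 207 giving 0.80. The missing success rates behind 207 are a separate gap, and they prevent any check of that base.

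Severity is minor to moderate. No endpoint, test or patient protection is affected, but the primary sample-size statement is inconsistent with itself and leaves the stopping point for accrual open.

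**What to change.** First decide what 248 counts, and say so in both Statistical Analysis and Participant Selection / Eligibility. Then restate the figures to match.

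- **If 248 is consented patients**, choose one of three statements:
  - give the screening number as about 259 for 207 randomised, or 260 for 208 in equal arms;
  - keep 248 and state that a 20% failure rate yields about 198 randomised, with power slightly below 0.80 (about 0.78 if 207 gives 0.80);
  - keep 248 and 207, and state that the allowance covers a 16.5% failure rate.
- **If 248 is randomised patients**, remove the screen-failure wording and restate the power at 248 (about 0.87 if 207 gives 0.80).

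Before any power figure other than 0.80 is written into the protocol, it should be computed from the success rates that produced 207, and those rates should be stated.

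The cost is about two sentences. Raising the screening number adds 11 or 12 consents (259 − 248 or 260 − 248); the other options add none. The design does not change.

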This is a prospective, randomized, unblinded trial performed at Lahey Hospital and Medical Center. All procedures will be performed by experienced advanced endoscopists with over 2000 career ERCP's and 350 ERCP's performed per year, (or by the advanced endoscopy fellow under supervision of the attending gastroenterologist). Enrolled patients will be randomly assigned by a computer-generated number list to 2 groups (group 1, angled-tip GW; group 2, straight-tip GW). All procedures will be performed using standard duodenoscope or Exalt duodenoscope (JF-260V; Olympus Medical Systems Corp, Tokyo, Japan). For the procedure, patients will receive either general anesthesia or monitored anesthesia care as clinically indicated. Medications will be administered by a licensed anesthesiologist or CRNA. All procedures will be performed via short-wire technique using a 0.025-inch, 260cm-long angled guidewire with 5-cm hydrophilic tip (Jagwire Revolution, Boston Scientific, Natick, MA) or a 0.025-inch, 260-cm long straight guidewire with a 5-cm hydrophilic tip. (Jagwire, Boston Scientific, Natick, MA) For cannulation, attending gastroenterologists will be allowed 5 minutes to cannulate (from first contact of ampulla) or 5 passes inadvertently into the pancreatic duct (whichever occurs first). If the procedure is performed by gastroenterology fellow, the fellow will be allowed 5 minutes from first contact with the ampulla or 5 passes into the pancreatic duct (whichever occurs first). If the pancreatic duct is cannulated, double guide-wire technique will be performed with the same wire (0.025-inch guidewire) for an additional 5 minutes. If cannulation remains unsuccessful, needle-knife technique will be performed with pancreatic duct stenting performed. This protocol is similar to Vihervaara et al.² Post-procedurally, patients will be monitored for post-ERCP pancreatitis with either inpatient follow-up or via a phone call if procedure performed as outpatient. Post-ERCP pancreatitis will be defined as new or worsened abdominal pain combined with >3 times the normal value of lipase more than 24 hours after ERCP and requirement of hospital admission or prolongation of a planned admission. Routine blood work will be collected upon admission and during hospitalization as clinically warranted. Data will be collected using the REDCap data collection application and will be securely stored on LHMC secured servers.

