Study Title: Comparison between angled-tip and straight-tip guidewire in biliary cannulation: A prospective, randomized trial

Protocol Version Number: Version 1.0 Protocol Date: 08/29/2022

Standard of Care: Procedure in both treatment groups is considered standard of care as they use FDA approved devices. Here at Lahey, The endoscopists use both guidewires. The guidewire is selected based on physician preference. While they typically start with a straight-tip wire, they would also use angled-tip guidewire if the straight tip guidewire does not achieve cannulation of the bile duct. Data shows that both guidewires are safe to use with similar rates of successful cannulation and adverse events.

Study Calendar / Schematic / Schedule

The main study-required visit will be the day of the planned procedure (ERCP). On this visit, the pre-procedural process will include a discussion with the patient regarding the risks and benefits of the procedure as well as a description of the study and consent for participation in the study. Pre-procedure data will be collected and entered into the data capture tool. The data collected will include patient demographics and indication for procedure. Randomization will then be performed immediately prior to the start of the planned procedure and the randomization assignment will be entered into the data capture tool. Data will then be collected immediately after the procedure and will include procedure duration, successful cannulation determination, pancreatic duct cannulation determination, types of guidewires used during procedure, fellows involvement in procedure and complications of procedure. On post-procedure day one to post procedure day five, post-procedural data will be collected by either inpatient assessment or by a telephone call to the subject if the procedure was performed on an outpatient basis by either the PI or sub-investigators. If there is a concern for possible post-ERCP pancreatitis, a lipase level will be checked on an inpatient or outpatient basis. There will be no other planned study-required visits after post-procedure day five. Subjects will be removed from enrollment if they choose to withdraw from the study.

Potential Risks and Discomforts

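### Fellow involvement is named as a predictor, but it has no stated role in allocation or the primary test and is listed for recording only after the unblinded procedure

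*Combined protocol and SAP*

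**What the plan says.** The Statistical Analysis section states that "Predictor variables include co-morbidities, indication for procedure and fellow involvement in procedure". It then gives three kinds of comparison: chi-squared tests for successful cannulation and for pancreatitis, and a t-test or Wilcoxon test for procedure duration. None of them uses a predictor variable, and no regression or stratified test is described.

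Allocation is described twice. Subject Enrollment says "The patient will be randomized to a study arm in a 1:1 fashion by a computer-generated random number list", run through REDCap. Study Design and Procedures says "Enrolled patients will be randomly assigned by a computer-generated number list to 2 groups". Neither mentions strata or blocks.

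Study Design and Procedures also states "This is a prospective, randomized, unblinded trial performed at Lahey Hospital and Medical Center". Procedures are done by endoscopists with more than 2000 career ERCPs, "or by the advanced endoscopy fellow under supervision of the attending gastroenterologist". There is no rule for who starts, no definition of involvement, and no statement of how a hand-over from fellow to attending is classified.

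On timing, the Study Calendar section says of the pre-procedure step: "The data collected will include patient demographics and indication for procedure". Next, "Randomization will then be performed immediately prior to the start of the planned procedure". The data collected after the procedure include "types of guidewires used during procedure, fellows involvement in procedure and complications of procedure".

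**The concern.** Operators range from a fellow in training to endoscopists with long experience, and the plan itself expects this to predict success. Two things follow.

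First, if operator experience affects success, an analysis that ignores it has less power than one that uses it. A chance difference in fellow share between the arms also adds noise to the estimated wire effect.

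Second, the wire is known before the procedure starts, and the protocol does not say whether the operator has been settled by then. Who starts, or when the attending takes over, could depend on the wire. Fellow involvement recorded after the procedure might then be partly a result of the allocation. Adjusting for it could introduce bias, while leaving it out would leave the difference uncorrected. As planned, the data could not separate the two situations.

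**Working it through.** **The plan's own figure.** The protocol gives 248 as 207 × 1.2, and 207 × 1.2 = 248.4, so the inflation step reproduces. The base of 207 cannot be checked, because no success rates or effect size are given. Nothing below depends on how 207 was reached.

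**Inputs from the protocol.** N = 207 before inflation (248 after), 1:1 allocation, significance at p < 0.05 (two-sided assumed), unadjusted chi-squared test.

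**Assumed inputs (not in the protocol).** Fellow share f of 20%, 30% or 50%. Attending success of 85% with the straight wire. Fellow success 10, 20 or 30 points lower. A wire effect of 12 points for power, the same for fellows and attendings. Simple randomisation, since no strata are stated.

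**Step 1: chance imbalance in fellow share.** SD = sqrt(f(1 − f) × 4/N).

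| f | SD, N = 207 | 95% range | P(gap > 10 points), N = 207 | P(gap > 10 points), N = 248 |
|---|---|---|---|---|
| 20% | sqrt(0.16 × 4/207) = 5.56 points | ±10.9 | 7% | 5% |
| 30% | sqrt(0.21 × 4/207) = 6.37 points | ±12.5 | 12% | 9% |
| 50% | sqrt(0.25 × 4/207) = 6.95 points | ±13.6 | 15% | 12% |

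A share of 50% is the worst case.

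**Step 2: effect on the estimate.** Shift = imbalance × success gap. At the 95% limits with N = 207, it runs from 10.9 × 0.10 = 1.1 points to 13.6 × 0.30 = 4.1 points. For scale, at 80% overall success the standard error of the difference is sqrt(2 × 0.80 × 0.20/103.5) = 5.6 points, which already includes this source of variation.

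**Step 3: validity and power.** Simulation with 40,000 runs per scenario and 103 patients per arm. With no wire effect and imbalance by chance only, the planned test rejects in 4.8% to 5.1% of runs. Power with the 12-point effect:

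| Fellow share | Success gap | Simple allocation, chi-squared | Simple allocation, CMH | Stratified allocation, CMH |
|---|---|---|---|---|
| 30% | 10 | 78.5% | 78.8% | 78.5% |
| 30% | 20 | 68.8% | 71.6% | 71.8% |
| 30% | 30 | 61.8% | 67.9% | 67.8% |
| 50% | 10 | 71.9% | 72.4% | 72.7% |
| 50% | 20 | 59.5% | 62.4% | 62.9% |
| 50% | 30 | 52.1% | 57.4% | 57.7% |

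The gain over the planned approach is 0 to about 6 points. Nearly all of it comes from the stratified (CMH, Cochran-Mantel-Haenszel) analysis and little from stratifying the allocation. Stratifying the allocation while keeping the plain chi-squared test makes that test conservative, with type I error of 3.7% to 4.9%. The two changes therefore belong together.

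**Step 4: if operator choice followed the arm (hypothetical).** With no wire effect and the same success assumptions:

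- Fellow share 45% v 55%: shift of 1 to 3 points (10 × 0.10 to 10 × 0.30), type I error 5.5% to 7.7%.
- Fellow share 40% v 60%: shift of 2 to 6 points (20 × 0.10 to 20 × 0.30), type I error 6.5% to 15.9%.

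These show what such behaviour would do. They are not evidence that it will occur.

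**The case against.** The strongest reply is that a single-centre trial with simple randomisation and a chi-squared test is valid as it stands. Randomisation allows for chance imbalance, and step 3 confirms it. Stratification and adjustment are good practice rather than a condition of validity. This stands, and it limits the first part of the concern to precision.

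Second, recorded after the procedure does not mean decided after assignment. The fellow's role may be fixed by the day's schedule before the wire is known. Attendings and fellows are also given the same time and pass limits in both arms, which constrains arm-dependent hand-over, although it does not exclude earlier take-over. This stands too: dependence on the arm is possible, not shown. It does not answer the point that the planned records could not reveal such dependence.

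Third, the protocol is silent on strata; it does not say that the list is unstratified. The supportable statement is that no stratification is stated.

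A reader might also infer that the plan will adjust for findings that emerge only after randomisation, because its potential confounders include an aetiology that differs from the suspected diagnosis and unforeseen pathology. The protocol lists these but specifies no adjusted model, so this is not a fault in the planned analysis.

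**Conclusion.** The point holds as an omission worth correcting. The plan names fellow involvement as a predictor, gives it no stated part in allocation or analysis, does not define it, and schedules its recording only after an unblinded procedure. Confidence in that is high, because it rests on the text.

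The definite cost is modest: 0 to about 6 power points under the assumed shares and success gaps, neither of which is in the protocol. If the fellow share is lower or the gap small, the cost is close to nothing.

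A reader might conclude that the primary comparison is biased or invalid. The documents do not support this. Chance imbalance leaves type I error near 5%, and nothing shows that operators will be chosen according to the wire. What remains is an open route to bias of unknown size. It can be narrowed cheaply before assignment, but it could not be soundly repaired later using involvement as recorded after the procedure.

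**What to change.** - Record the intended first operator (fellow or attending) in REDCap before assignment. Define what counts as fellow involvement.
- Stratify the allocation table by intended first operator, with permuted blocks of varying size.
- Make the primary analysis match: a Cochran-Mantel-Haenszel test with a stratified risk difference, using the intended operator as recorded before assignment.
- Limit any further adjusted model to variables recorded before assignment, such as planned indication. Papilla type is not among the data listed before randomisation and should stay out unless it is documented before assignment.
- Report hand-over from fellow to attending descriptively by arm, and do not use it as a covariate.

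If enrolment has begun, record the intended operator from now on and pre-specify the stratified analysis of those patients as supportive.

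The cost is one extra field, a new allocation table, and the discipline of naming the operator before the wire is known. No additional patients are needed.

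### The primary test leaves out the pre-procedure indication recorded before randomisation: a valid test, with a small loss of precision

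*Combined protocol and SAP*

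**What the plan says.** The primary analysis is one sentence in Statistical Analysis: "The proportion of procedures that are successful in the two treatment arms will be compared using chi squared analysis". The endpoint is met by "showing a statistically significant difference in the rate of successful cannulation", with significance "as defined as a p-value of less than 0.05"; sidedness is not stated. No adjusted model, stratified test or covariate-based sensitivity analysis is described. Subject Enrollment gives 1:1 allocation from a computer-generated list and mentions no stratification factor.

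On covariates, the Study Calendar section says of the pre-procedure data: "The data collected will include patient demographics and indication for procedure". Randomisation comes after that entry. Statistical Analysis then says: "Predictor variables include co-morbidities, indication for procedure and fellow involvement in procedure". Its list of potential confounders begins with the anatomy of the papilla and continues with "underlying etiology of biliary obstruction (which may be different from suspected pre-procedure diagnosis) or unforeseen biliary pathology which alters procedure". The plan does not say how any predictor or confounder will be used, or when etiology and pathology are recorded.

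On size: "The sample size needed to achieve statistical significance for the primary outcome is 248 (207 *1.2) after adding 20% screen failure rate", and "The power of the study to detect if there is a true difference will be 0.80". No success rates or target difference are given.

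**The concern.** Indication is on record before the wire is assigned, so the wire cannot affect it. If it predicts success, as the plan supposes, stratifying on it removes some outcome variation and corrects for chance imbalance between the arms. The plan collects the variable and then makes no use of it.

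A second, smaller matter is the confounder list. The plan itself separates etiology from the suspected pre-procedure diagnosis and calls the pathology unforeseen, so neither need be known at randomisation. The inclusion criteria cover ERCP for cholangiography and for bile or tissue sampling, so this information may arrive only once the duct has been entered. That timing is an inference. A covariate known mainly when cannulation succeeds partly records the outcome, and adjusting for it can distort the comparison of wires. The plan proposes no such adjustment, but calling these variables confounders without stating a use leaves it open.

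**Working it through.** **The plan's own figure.** 207 × 1.2 = 248.4, stated as 248. The base of 207 cannot be re-derived because no success rates are given. Nothing below changes either figure.

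**Step 1: precision from adjusting for indication.** The rates are assumptions: a share h of patients has a harder indication (0.3, 0.4 or 0.5), with success 0.90 in the easier group (p_e) and 0.80, 0.70 or 0.60 in the harder group (p_h). The ratio of within-group to total variance is

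R = [(1−h)·p_e(1−p_e) + h·p_h(1−p_h)] / [p(1−p)], where p = (1−h)·p_e + h·p_h.

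The equivalent number of extra patients is 207/R − 207. For example, with h = 0.4 and p_h = 0.60, R = (0.054 + 0.096)/(0.78 × 0.22) = 0.150/0.1716 = 0.874, and 207/0.874 − 207 is about 30.

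| h | p_h = 0.80 | p_h = 0.70 | p_h = 0.60 |
|---|---|---|---|
| 0.3 | 0.981 (3.9 patients) | 0.938 (13.8) | 0.877 (29.0) |
| 0.4 | 0.980 (4.2) | 0.935 (14.4) | 0.874 (29.8) |
| 0.5 | 0.980 (4.1) | 0.938 (13.8) | 0.880 (28.2) |

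The variance reduction is therefore about 2-13%, or 4-30 patients.

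**Step 2: chance imbalance.** With 103.5 patients per arm, the standard deviation of the between-arm difference in h is √[h(1−h)·2/103.5]. This is 0.064 at h = 0.3 and 0.070 at h = 0.5. An imbalance of 10 points or more then has probability about 0.12 to 0.15. It moves the crude difference by 0.10 × 0.10 = 1 point up to 0.10 × 0.30 = 3 points. This is random error that the test's error rate already covers; it is not bias.

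**Step 3: power.** Simulation with 20,000 runs, 207 patients, two-sided 0.05 (assumed), 40% with the harder indication, and odds ratio (OR) for success 0.5, 0.33 or 0.2. Control success is 75%, 80% or 85%, with differences of 14.8, 13.2 and 11.3 points, which are those giving 80% power at 207. Each cell shows power (%) for chi-squared, then for Cochran-Mantel-Haenszel stratified by indication.

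| Success, control v angled | OR 0.5 | OR 0.33 | OR 0.2 |
|---|---|---|---|
| 75.0% v 89.8% | 81.8, 82.0 | 80.9, 81.9 | 81.6, 84.2 |
| 80.0% v 93.2% | 81.7, 81.7 | 82.1, 82.9 | 82.4, 84.4 |
| 85.0% v 96.3% | 82.6, 82.9 | 82.8, 83.7 | 82.5, 84.1 |

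The gain runs from 0 to 2.6 points. With no difference between wires, both tests reject in 4.8% to 5.2% of runs.

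**Step 4: illustration of a late-learned covariate.** Assume 30% have a hard etiology, with success 75% (angled) v 60% (straight) in hard cases and 92% in both arms otherwise. The true difference is (0.644 + 0.225) − (0.644 + 0.180) = 4.5 points. Let q be the share of failed hard cases in which the etiology is learned; the rest keep an easier presumed diagnosis. The fractions recorded as hard are 0.225 + 0.075q and 0.180 + 0.120q. Each stratum has Mantel-Haenszel weight ab/(a+b), where a and b are the two arm fractions.

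At q = 0, every recorded hard case is a success (difference 0, weight 0.225 × 0.180/0.405 = 0.100). The rest give 0.644/0.775 − 0.644/0.820 = 4.56 points (weight 0.775 × 0.820/1.595 = 0.398). Pooled: 0.398 × 4.56/0.498 = 3.6 points.

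| q | Pooled difference (points) | Difference in recorded hard group (points) |
|---|---|---|
| 0% | 3.6 | 0 |
| 25% | 4.3 | 6.6 |
| 50% | 4.6 | 10.7 |
| 80% | 4.7 | 13.7 |
| 100% | 4.5 | 15 |

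**The case against.** The strongest reply is that nothing is broken. An unadjusted chi-squared test is valid in a 1:1 randomised trial. Leaving out indication neither biases the comparison nor inflates the false-positive rate. The link between indication and success is assumed, since the documents give no rates, and at a 10-point gap the gain is only about 4 patients. All of this stands, and it limits the point to precision.

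It can also be asked why indication should be chosen over the other named predictors. The Study Calendar answers this: fellow involvement is among the data collected after the procedure, and co-morbidities are not in its pre-procedure list. Of the three, only indication is explicitly placed before randomisation.

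A reader might go further and infer that the plan will adjust for final etiology and unforeseen pathology, and that its result will be biased. The documents do not support that.

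- No adjustment for these variables is proposed anywhere.
- The 3.6-point figure and the absent effect in hard cases arise only if etiology is learned in no failed hard case. Study Design and Procedures provides for double-guidewire and needle-knife techniques when the initial attempt does not succeed. Successful cannulation is not defined, so the duct may be entered in some patients counted as failures.
- Papilla anatomy heads the confounder list and is the subject of a secondary question. It can be seen without entering the duct, so the timing objection does not reach it.

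**Conclusion.** The point holds as a modest, low-cost improvement. The planned primary test is sound, but it leaves unused a baseline variable that the plan both collects and names as a predictor. On the assumed rates, adjustment is worth about 2-13% of variance, or 4-30 patients on 207, and 0 to 2.6 points of power. If indication is only weakly related to success, the gain is close to nil.

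The matter of late-learned covariates is a safeguard against a later choice and does not describe a fault in the stated analysis. Any bias would depend on how often etiology is learned in failed cases, which the documents do not say. In the illustration the pooled distortion is 0.9 points at the extreme (4.5 − 3.6) and at most 0.2 points once q reaches 25%, although the hard-group estimate stays too low for longer.

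**What to change.** In Statistical Analysis, prespecify a risk difference with 95% CI adjusted for pre-procedure indication in two or three named groups, by Mantel-Haenszel or by a logistic model with standardisation. Report the unadjusted chi-squared test alongside it, and state which result decides the primary question.

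Add a sentence saying that any adjustment of the primary comparison uses only variables recorded before randomisation, and that final etiology and unforeseen pathology are reported descriptively. The planned comparison by papilla type is a separate question and can stay.

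The cost is SAP wording: no new data and no change to the sample size. The one real constraint is that the groups must be fixed before analysis and kept few, because failures may be few and small groups would make the adjusted estimate unstable.
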